Data that links participants to information collected in the course of a given study will be kept separately from identifying information in an electronic, password-protected MS Access database stored at duhsnas-pri\dusom_psych\private\[name] Research Lab\mCM for Alcohol and Smoking; the key connecting identifying information and data will be stored here as well. Hard copy paper records will be stored in a locked filing cabinet in the study coordinator's locked office, within [name] laboratory space at Duke University Medical Center South. Information from the interview and/or questionnaires may be entered into a computerized database that will be stored on the DUMC server at duhsnas-pri\dusom_psych\private\[name] Research Lab\mCM for Alcohol and Smoking in a password-protected database separate from the "logbook" of identifying information. This database is accessible only by [name] and study staff. Any staff members who leave the study for any reason will have access to study resources, including data, removed immediately.

The study's safety monitoring plan is based on long-term clinical and research experience with patients with psychiatric illness, and is explained in more detail in the "Data and Safety Monitoring Plan" section. All project staff will complete educational units required by Duke's IRB, including CITI training and DSRT training.

Staff Training

Of the measures in this study, only the SCID and the qualitative data interview require specific training or skills for administration. As in our other studies, multiple SCID diagnostic raters will be utilized over the data collection period. Each rater will be trained using SCID standardized training (i.e., manual, videotapes, and co-rating training with a trained rater). Interrater reliability for diagnoses based on videotapes of patient interviews across previous studies has been high with a kappa = .96. Additionally, staff providing these diagnostic interviews are trained in use of the Psychiatric Emergency Standards of Practice. Training is completed and supervised by a Master's level clinician with experience in psychiatric diagnosis, or by Ph.D. level clinical psychologists. Regular clinical supervision is provided on a monthly basis in team meetings, and consultation is provided regularly to interviewers.

The qualitative data interview will be administered by an experienced clinical interviewer with an advanced degree (masters or doctoral). Interview sessions will be audio recorded to permit detailed analysis of participant comments and ensure that interviews are conducted skillfully and with respect for participant rights. Audio recordings are made using an encrypted iPad or iPhone; see "Protection Against Risk and Data Security Measures" herein.

Data and Safety Monitoring Plan

Quitting smoking and alcohol use should enhance rather than jeopardize health status, and potential serious adverse events (SAEs) for participants in this project are not expected. Regardless, we will minimize potential risk by careful screening of potential participants (e.g., medical clearance by their primary care provider if there are contraindications to smoking cessation pharmacotherapy).

The individuals responsible for data safety and monitoring will be the PI, the project manager, and the Study Physician. The Study Physician for this trial will be [name]., Ph.D. [name] is a board certified general psychiatrist, and is the treating physician of the local VA Medical Center's specialty smoking cessation clinic. As the Study Physician, [name] will ensure participants are medically cleared to participate in this trial and will review all reports of adverse events (AEs) sent by the study coordinator and evaluate the patient as necessary to determine whether there is any corrective action needed.

Further data safety and monitoring will be provided by the PI. There will be several ongoing mechanisms for monitoring and reporting of AEs: 1) ongoing participant contact via study personnel, 2) a phone number provided to participants to report concerns related to study participation; 3) weekly meetings between the PIs and study personnel.

The PI will meet at least weekly with study personnel to discuss participants' reactions to the intervention, proper delivery of the intervention, and any adverse events or unanticipated problems. Regular meetings between investigators and the project manager will allow for ongoing progress reports, including the number of participants currently involved in the study groups, attrition rates, and scheduled data collection from participants, as well as notification and review of any AEs. Safety monitoring for AEs will be conducted in real time by the PI and/or project manager. The following information about adverse events will be collected: 1) the onset and resolution of the AE, 2) an assessment of the severity or intensity (use existing grading scales whenever possible), 3) an assessment of the relationship of the event to the study (definitely, probably, possibly or not related), and 4) action taken (e.g., none, referral to physician, start or increase concomitant medication). The PI will determine the severity of the event, will assign attribution to the event, and will monitor the event until its resolution. Any adverse events will be reported to the IRB in accordance with the IRB guidelines.

Plans for Responding to a Participant Who Expresses Suicidal Ideation

Our research laboratory has established, DUMC IRB-approved standards of practice for the evaluation of risk of suicide and homicide. The policy includes a thorough risk assessment including evaluation of risk factors and protective factors associated with both suicide and homicide. Also included in the policy are differential recommendations for action based on determinations of low, moderate, or high risk. Any staff member conducting an interview in which moderate or high risk is determined will contact a senior staff person with clinical expertise in risk assessment.

Outcome Measurement and Biochemical Verification

Self-reported and bioverified prolonged abstinence from alcohol, smoking, and dual abstinence at the 6-month follow-up will be the primary end-point. Prolonged abstinence will exclude substance use in the first two weeks following the quit date to give participants time to achieve initial abstinence (Hughes et al., 2003). Self-reported prolonged abstinence will be verified by breathalyzer alcohol assessment and assay of cotinine, a metabolite of nicotine in the saliva. Saliva samples will be collected from participants at end of treatment, and at 6-month follow-ups. Deidentified saliva samples will be sent to Salimetrics, and there they will be analyzed for the presence of cotinine using a standard cut point of 10 ng/ml to determine abstinence. A blind sample of 5% will be run again to assure test accuracy of saliva samples. All participants will be asked to provide saliva samples. However if it seems likely that they will have a positive saliva cotinine according to the Tobacco Exposure Questionnaire administered at end of

monitoring at 6-month follow-up, the collected sample may not be sent to Salimetrics for testing.

Participants will also report alcohol consumption patterns such as standard drinks/week, heavy drinking episodes (drinking enough so that BrAC would have reached 0.08g/dL), proportion of days abstinent, and achieving recommended drinking limits (≤ 14 drinks/wk and < 5 drinks/day for men; ≤ 7 drinks/wk and < 4 drinks/day for women). Because bioverification of long-term alcohol abstinence is not substantially more reliable than self-report (Babor, Steinberg, Anton, & Del Boca, 2000), alcohol outcomes will primarily be assessed with self-report. Participants will provide breathalyzer verification of alcohol abstinence at the end of Thinning mCM and 6-month follow-up visits. Participants will also report number of cigarettes smoked each day, and days of smoking abstinence. Collection of alcohol and smoking use data will allow for calculation of dual abstinence days and longest duration of dual abstinence. Participants will be asked to submit a saliva sample for biochemical validation. Saliva will be stored in a freezer in a locked office. At the end of the study, the project coordinator will personally mail all saliva samples to the appropriate laboratory to be analyzed for the presence of cotinine. The saliva will only be tested for cotinine, a by-product of nicotine. This method yields response rates that are comparable to in-person collection methods (i.e., 70%). A standard cut-point of 10 ng/ml will be used to discriminate those who are abstaining from those who are continuing smokers.

Prolonged abstinence from alcohol will be assessed using phosphatidylethanol (PEth) as a biomarker at the 6-month follow-up visit. While self-report abstinence has been a proven indicator, bioverification using PEth testing is an effective tool for identifying heavy drinking (Nanau & Neuman, 2015), and has a 99% sensitivity for detecting excessive alcohol consumption (Aradottir et al., 2006). This will be assessed using a dried blood spot collection, collecting 3 spots (about 3 mL) of blood from the participants' finger. PEth testing has been shown to have. The de-identified test card will be collected by ARCpoint labs of Raleigh Durham for analysis. All sharps and biohazardous material will be collected and disposed of by ARCPoint labs.

Data Analyses

Descriptive statistics will be used to summarize all study variables. For continuous variables, means, standard deviations, percentiles, ranges, box plots and histograms will be generated. For categorical variables, frequencies and proportions will be generated. We will construct individual and mean trajectory plots of the longitudinal outcome variables to understand their general trends over time (i.e., post-treatment, 6 weeks and 6 months). Differences in treatment outcomes will be tested via generalized linear modeling. In addition, we will explore the variability and correlation structure of longitudinal variables. We will examine all variables to determine if parametric distributional assumptions (e.g. normality for the continuous variables) are valid. Variables not meeting distributional assumptions will either be transformed or modeled

using nonparametric or semi-parametric methods (e.g. quasi-likelihood methods). In planning a full RCT of the tele-health mCM intervention for AUD and smoking, it is important to evaluate study feasibility and treatment procedures, as well as gain information about effects on proposed outcome variables.

Specific Aim 1: Develop a multi-component alcohol and smoking tele-health mCM intervention.

Content analysis of the cohort interviews will yield descriptive data regarding participants' perceptions of specific components of the treatment at each development phase. The first cohort will identify unanticipated problems with treatment procedures and equipment, clarify the change process and potentially identify new variables to examine as treatment mechanisms, and serve as a check on the appropriateness of the selected outcome measures. Participant feedback will also be critical in evaluating the user experience so that the phone app and phone counseling procedures can be enjoyable to the target population. Though the perspective of each participant in the first cohort will be strongly considered, negative feedback about an aspect of the intervention from one participant will be weighed against the feedback from others and the theoretical underpinnings of the treatment before the research team makes changes to the treatment. For example, if any participants note difficulty comprehending a treatment component or message, that component will be modified for clarity, as that does not conflict with the theoretical approach. Similarly, we will consider changes to the sequencing of phone counseling. PIs will meet weekly with the phone counselor to discuss narrative summaries of cases and the strengths and weaknesses of the treatment, as well as ease of manual use.

Specific Aim 2: Evaluate the feasibility and acceptability (e.g., mCM app reliability, mCM app procedures completion, patient satisfaction) of a tele-health mCM intervention; relative to a comparison group receiving a tele-health intervention without mCM.

We will additionally explore differences in alcohol and smoking abstinence outcomes by treatment. Because the tele-health only intervention is expected to have a uniformly small impact on alcohol and smoking outcomes in comparison to the tele-health mCM intervention, implementation of an imbalanced-samples design, with twice as many participants randomized to the tele-health mCM treatment as to the tele-health only treatment, should maximize power for identifying treatment effects. That said, the proposed sample has 80% power to detect a treatment effect equivalent to Cohen's $d = 0.76$. For reference, in our pilot study of 22 smokers with PTSD, tele-health mCM yielded an effect size of Cohen's $d = 0.79$ at the 3-month follow-up. In particular, comparisons by treatment at post-intervention, 6 week follow-up, and 6-month follow-up will be made regarding alcohol consumption (drinks/week, number of heavy drinking episodes, proportion of days abstinent, and achieving recommended drinking limits) and smoking (number of cigarettes smoked each day and number of days of smoking abstinence) *via*

generalized linear modeling, which can accommodate normally and non-normally distributed (e.g., count) variables.

References

- Acuff, S. F., & Murphy, J. G. (2017). Further examination of the temporal stability of alcohol demand. *Behavioural Processes, 141*, 33-41. doi:10.1016/j.beproc.2017.03.020.
- Alessi, S. M., & Petry, N. M. (2013). A randomized study of cellphone technology to reinforce alcohol abstinence in the natural environment. *Addiction, 108*(5), 900-909. doi:10.1111/add.12093
- drinking outcomes in clinical trials. *Journal of Studies on Alcohol, 61*, 55-63.
- Bechara. A., Damasio, A.R., Damasio, H., Anderson, S.W. (1994). Insensitivity to future consequences following damage to human prefrontal cortex. *Cognition, 50*, 7-15.

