Despite established short-term efficacy, CM has not been widely adopted to treat either AUD or smoking. One prominent concern is the long-term impact of CM after contingencies are removed. However, follow-up abstinence rates for CM treatments have been improved by the integration of CBT into CM (Carpenter et al., 2014; R. M. Kadden, Litt, Kabela-Cormier, & Petry, 2007). CM-induced abstinence could provide advantages to CBT alone, as it gives the individual a positive early experience with abstinence that 1) increases self-efficacy, 2) increases engagement in CBT, 3) provides the opportunity to practice CBT skills in time to acquire and utilize the coping skills provided by CBT, and 4) provides time for people to develop alternative reinforcers to substance use, and 5) engages people in CBT intervention that includes coping skills acquisition and home practice that encourages generalization of skills to the naturalistic environment, which likely contributes to the durability of CBT effects on substance use outcomes (Carroll et al., 2000; Carroll et al., 1994; O'Malley et al., 1996). There is evidence that CM can be used to treat comorbid substance use disorders, as a trial targeting only cocaine use in those who used both cocaine and opioids produced large and unexpected reductions in opioid use (Silverman et al., 1998). In addition, previous research has found that using CM can be effective in increasing simultaneous abstinence from multiple substances (Piotrowski et al., 1999).

There is a surprising lack of research aimed at evaluating multi-component interventions that integrate CM with evidence-based CBT and pharmacotherapy. The addition of CBT is critical because CM interventions alone have been limited in their ability to maintain behavior change after the removal of the contingency (Dallery & Raiff, 2012). With the inclusion of evidence-based CBT and a tele-health clinic for NRT, we will be able to

evaluate whether the tele-health mCM intervention keeps participants engaged in treatment, improves NRT adherence, reduces delay discounting (i.e., decreased subjective valuing of rewards that are temporally distant), and increases self-efficacy, all of which have been predictive of long term abstinence from both alcohol and tobacco.

Objectives:

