- have had substance use disorder (other than alcohol or nicotine) in the preceding 3 months
- are currently imprisoned or in psychiatric hospitalization

Table 1. Study Procedures

| Session # | Location of Visit | Procedures | Payment |
|-----------|-------------------|---|---------|
| 1 | Lab | Consent; psychiatric interview; questionnaires; urine drug screen and pregnancy test; carbon monoxide and breath alcohol readings | \$50 |

| 1-3 weeks | | | |
|-------------------------------------|-------|---|--|
| 2 | Phone | Counseling session 1 of 4 | n/a |
| 1 week | | | |
| 3 | Phone | Counseling session 2 of 4; begin practice mCM monitoring, begin bupropion if eligible | Up to \$34 for monitoring |
| 1 week | | | |
| 4 | Phone | QUIT DATE; counseling session 3 of 4; begin active mCM monitoring OR active mobile monitoring (MM); begin nicotine replacement therapy (NRT) | n/a |
| 2 weeks | | | |
| 5 | Phone | Counseling session 4 of 4; continue active mCM monitoring OR active mobile monitoring | n/a |
| 1 week | | | |
| 6 | Phone | Final week of abstinence induction in mCM group; MM group continues monitoring; questionnaires | Up to \$702 (mCM) OR \$132 (MM) for active monitoring; |
| | | | \$50 for assessment |
| 2 weeks | | | |
| 7 | Lab | End thinning (mCM group) OR mobile monitoring (MM group); return equipment; questionnaires; end NRT and bupropion; saliva sample; interview about treatment | Up to \$400 (mCM) OR \$88 (MM) for continuing monitoring |
| | | | \$35 for equipment return; \$50 for assessment; \$50 for saliva sample |
| 6 months after Session 4 | | | |
| 8 | Lab | Questionnaires; saliva sample; blood spot collection | \$50 for assessment and \$50 for saliva sample; \$50 for blood spot test |
| TOTAL COMPENSATION POSSIBLE: | | mCM Group Mobile Monitoring | \$1521* \$639* |

*because compensation depends partly on the number of alcohol breathalyzer prompts, it is possible that the total compensation will vary slightly.

Consent and Screening Procedures

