Pharmacotherapy for Smoking Cessation

Treatment will include standard pharmacotherapy for smoking cessation. This consists of bupropion, nicotine patch, and an 8-week course of < 2 rescue methods (e.g., nicotine gum, lozenge) in participants for whom these medications are not contraindicated or who receive medical clearance from a physician. Participants will be screened for suitability for NRT or other smoking cessation medication. Participants who report being contraindicated to bupropion or NRT (i.e. high blood pressure not controlled by medication) must obtain authorization from their physician prior to receiving the corresponding medication. If the patient does not have a physician, or the physician does not respond to information requests, [name] will make determinations about whether to authorize study medications. [name] will prescribe a tailored amount and delivery type of NRT based on number of cigarettes smoked per

day, quit history, medical conditions, and psychiatric comorbidities. NRT and bupropion will be provided *via* mail. [name] will write the NRT and/or bupropion prescriptions and work with other study staff and participants' primary care physician to discuss contraindications. Eligible participants will be provided bupropion for eight weeks. Participants will be informed that they can discuss whether or not to continue bupropion use for relapse prevention with their personal physician. At the end of the study's course of bupropion, participants will be reminded to confer with their physician re: continued bupropion use. For participants who relapse to smoking or are unable to quit, [name] will make decisions about whether to prescribe additional NRT to assist the participant in their continued attempts to stop smoking.

6-Month Follow-Up

All participants will be asked to provide a saliva sample to bioverify smoking abstinence. Alcohol abstinence will be measured by self-report, breathalyzer, and a blood spot sample that measures PEth at the 6-month follow-up. Participants will be encouraged to attend the 6-month follow-up assessment in the lab. However, if participants are unable due to transportation issues or decline to attend the 6-month follow-up, we will administer interview and questionnaire measures by phone and collect saliva samples by mail.

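### At end of treatment, smoking abstinence is judged by saliva cotinine with no rule for users of study nicotine replacement, at the visit where Table 1 ends that treatment

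*Combined protocol and SAP*

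**What the plan says.** All references are to the combined protocol and SAP.

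- **Outcome Measurement and Biochemical Verification.** Saliva is taken at end of treatment and at 6 months and is "analyzed for the presence of cotinine using a standard cut point of 10 ng/ml to determine abstinence". The section adds "The saliva will only be tested for cotinine, a by-product of nicotine", and then "A standard cut-point of 10 ng/ml will be used to discriminate those who are abstaining from those who are continuing smokers". It states no condition for people using NRT. Samples judged likely to be positive from a questionnaire may go unassayed, and their coding is not given.
- **Table 1, Study Procedures.** NRT starts at Session 4, the quit date. Session 7 lists "return equipment; questionnaires; end NRT and bupropion; saliva sample; interview about treatment".
- **Pharmacotherapy for Smoking Cessation.** Standard treatment is bupropion, nicotine patch and "an 8-week course of < 2 rescue methods (e.g., nicotine gum, lozenge". No separate patch duration is given. The study physician may prescribe further NRT to people who relapse or cannot quit.
- **Treatment Process Measures.** NRT and other cessation-aid use is recorded at each follow-up.
- **Mobile CM Procedures.** CO is read twice a day through the app. Below 6 ppm (after the first week) is the abstinence criterion for payment in the mCM group. Under Study Design, the comparison arm is monitored on the same schedule.
- **Primary end-point.** Self-reported and bioverified prolonged abstinence at 6 months.

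**The concern.** The protocol itself describes cotinine as coming from nicotine, and NRT supplies nicotine. A participant who has stopped smoking and takes study NRT up to Session 7 may exceed the cut-point and, by the rule as written, be classed as a continuing smoker. The participants most exposed to this error are abstainers who adhere to the treatment provided.

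The error need not be equal between arms. The Background says the study will "evaluate whether the tele-health mCM intervention keeps participants engaged in treatment, improves NRT adherence". If adherence among abstainers turned out higher with mCM, more of them would fail the test and the comparison would be tilted against mCM. Data Analyses presents the pilot as a source of information on outcome effects for a full trial, and a verified end-of-treatment rate carrying this error would be a poor planning input.

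**Working it through.** **Timing (from Table 1)**

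- Session 4 to Session 7: 2 + 1 + 2 = 5 weeks. This reproduces the 5 weeks post-quit given for the end of Thinning in the mCM intervention section.
- Table 1 reading: NRT ends at week 5, so the gap between NRT and the Session 7 sample is 0 weeks.
- Pharmacotherapy reading, counting the 8-week rescue course from the quit date: 8 − 5 = 3 weeks of NRT remain at Session 7.
- Session 8 is 6 months after Session 4, taken as 26 weeks. The gap from planned NRT to the 6-month sample is 26 − 5 = 21 weeks or 26 − 8 = 18 weeks.

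On either reading the Session 7 sample is taken during NRT or on the day it ends. On neither does the planned course reach 6 months.

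**What the rule can tell at Session 7**

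A value below 10 ng/ml still supports abstinence. A value above it is compatible with smoking, with NRT, or with both. Recorded NRT use could separate some of these cases, but no rule connects it to the classification.

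**Size (illustration; every rate is assumed)**

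Let p be true abstinence and q the share of abstainers who are cotinine-positive from NRT, with all smokers positive. The verified rate is p(1 − q). Take p = 50% (mCM) and 20% (comparison), a true difference of 30 points.

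| q mCM | q comparison | Verified rates | Difference |
|---|---|---|---|
| 25% | 25% | 37.5% vs 15% | 22.5 |
| 50% | 50% | 25% vs 10% | 15 |
| 75% | 75% | 12.5% vs 5% | 7.5 |
| 60% | 40% | 20% vs 12% | 8 |
| 80% | 40% | 10% vs 12% | −2 |
| 40% | 60% | 30% vs 8% | 22 |
| 25% | 75% | 37.5% vs 5% | 32.5 |

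With equal q the difference shrinks by the factor (1 − q). It is overstated only if 0.20 × q(comparison) exceeds 0.50 × q(mCM), that is, if the comparison share is more than 2.5 times the mCM share. With no true effect (30% in both arms), q of 60% vs 40% gives 12% − 18% = −6 points, and the reverse gives +6.

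**The same check on CO as a replacement**

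Let f be the share of smokers who pass a CO reading. The verified rate is p + (1 − p)f.

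- f of 30% (mCM) vs 10%: 0.50 + 0.50 × 0.30 = 65% and 0.20 + 0.80 × 0.10 = 28%, a difference of 37 points against a true 30.
- The same f with 30% true abstinence in both arms: 0.30 + 0.70 × 0.30 = 51% and 0.30 + 0.70 × 0.10 = 37%, a false +14.
- f reversed (10% vs 30%): 55% vs 44%, 11 points against a true 30. With no effect, 37% vs 51%, a false −14.

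CO removes the NRT problem but can introduce an error between arms of its own.

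**The case against.** The strongest reply is that little depends on this result. The primary end-point is at 6 months. The smoking variables named under Specific Aim 2 (cigarettes per day, days abstinent) are self-reported, and abstinence comparisons there are exploratory. With 15 comparison participants, one person is 100/15 = 6.7 points, so a false 6 points is less than one person. At 50% vs 20% the 95% half-width is already 1.96 × √(0.25/30 + 0.16/15) = 27 points. This stands, and it is why the point is minor.

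Second, cotinine is not the only smoking information at end of treatment: both arms give CO readings through the app on one schedule. That is true of the data collected. The stated verification rule nevertheless names cotinine only, and the 6 ppm figure appears only where payment is set.

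Third, CO is not clearly better. The calculation above supports this, and a single reading cannot verify the 7-day and 30-day abstinence listed in Table 2. CO should therefore support self-report, with its limits stated.

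Three stronger readings are tempting, and the documents do not support them:

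- **That the primary end-point is compromised.** Planned NRT is over 18 to 21 weeks earlier. The remaining uncertainty is that the text never says Session 7 saliva is excluded from verifying prolonged abstinence. Further NRT is possible after relapse, which justifies a sensitivity analysis but does not show a bias.
- **That the rule is biased against mCM.** Better NRT adherence with mCM is a question the study poses. It is not a finding.
- **That unassayed samples leave the end-point undefined for everyone.** People who report smoking already fail an end-point that requires self-reported abstinence. The gap concerns only self-reported abstainers who are predicted to be positive.

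**Conclusion.** The point holds in a limited form and is minor. Followed as written, the Session 7 rule can class abstinent NRT users as continuing smokers, so end-of-treatment verified smoking abstinence, and dual abstinence with it, can be understated. This follows from the protocol's own timing and its own description of cotinine.

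The size and the direction between arms are unknown. They depend on NRT use at Session 7 and on cotinine levels during NRT, and the documents give neither. The figures above show what assumed rates would do and are not estimates.

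The conclusion that the 6-month end-point is unaffected rests on two conditions: that NRT follows one of the two planned courses, and that Session 7 saliva plays no part in verifying that end-point. Table 1 and the pharmacotherapy section do not agree on when NRT ends, and they must be reconciled.

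**What to change.** 1. **Session 7.** State that cotinine above 10 ng/ml does not by itself class a participant as smoking if recent nicotine-product use is reported. Report end-of-treatment abstinence as self-report supported by CO below 6 ppm, judged by the same rule in both arms. The CO can come from the app readings already taken on a common schedule (name which ones in advance) or from one staff-observed reading at the lab visit. Say that 6 ppm then serves as an outcome threshold. Give the cotinine-only classification as a sensitivity analysis.
2. **6 months.** State that Session 7 saliva does not verify the primary end-point. Keep cotinine at 6 months, with a sensitivity analysis for reported nicotine-product use.
3. **Unassayed samples.** At 6 months, assay the samples of all self-reported abstainers.
4. **NRT dates.** Reconcile Table 1 with the pharmacotherapy section.

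**Cost.** This is mostly analysis wording. NRT use and app CO are already collected. If a lab reading is preferred, Session 7 is already a lab visit, and the plan already says "Participants will provide breathalyzer verification of alcohol abstinence at the end of Thinning mCM and 6-month follow-up visits". Some further 6-month assays may be needed.

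**Downsides to state in the plan.** CO has a short look-back and cannot verify 7-day or 30-day abstinence. Only mCM participants are paid for readings below 6 ppm, so the share of smokers who pass may differ by arm and bias the comparison in either direction. End-of-treatment and 6-month verified rates would rest on different tests and should not be compared directly.
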